## 9 STATISTICAL METHODS

### 9.1 Sample size calculations

For the parallel cluster study in Phase 1, the primary analysis will evaluate whether the use of ePOCT+ for case management of sick children in PHC facilities results in decreased antibiotic prescriptions (superiority analysis) at the initial consultation. Superiority in antibiotic prescription is defined as a relative decrease of  $\geq 25\%$  in the proportion of children prescribed an antibiotic. We estimated a cluster size of 660 patients (monthly utilization of 220 – accounting for up to 30% non-adherence from 315 – over 3 months) and an intraclass correlation coefficient of 0.025. Non-adherence here is defined as HWs not using the application for all eligible patients that come to the HF for various reasons. To have 80% power to detect a 25% reduction in antibiotic prescription (e.g. from 35% to 26%), for a one-sided hypothesis test at alpha of 0.05, we would require a minimum of 11 clusters per arm. With 16 clusters (or HF) over 3 months, we expect a total of 10,500 participants per arm, this sample size is

sufficient to test for non-inferiority in the secondary outcome (clinical cure at day 7) between the control and intervention groups.

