3.3 Sample size

The primary analysis will evaluate whether the use of ePOCT+ for case management of sick children in PHC facilities results in decreased antibiotic prescriptions (superiority analysis) at the initial consultation. Superiority in antibiotic prescription is defined as a relative decrease of $\geq 25\%$ in the proportion of children prescribed an antibiotic. We estimated a cluster size of 660 patients (monthly utilization of 220 – accounting for up to 30% non-adherence and/or loss to follow-up from 315 – over 3 months) and an intraclass correlation coefficient of 0.025. Non-adherence here is defined as HWs not using the application for all eligible patients that come to the HF for various reasons. To have 80% power to detect a 25% reduction in antibiotic prescription (from 35% to 26%), for a two-sided hypothesis test at alpha of

0.05, we would require a minimum of 11 clusters per arm. With 16 clusters per arm, over 3 months, we expect a total of 10,500 children in each study arm. Considering the pragmatic/adaptive nature of the study design, if a higher antibiotic prescription in the control arm is encountered (e.g. 45% or higher), each cluster study of 5-6 health facilities per study arm will be sufficiently powered to show a statistically significant reduction in the primary outcome. Sample size calculations were performed in R statistical software (version 4.0.3) using the CRTSize package (Rotondi, 2015).

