6.1 Analysis methods

Analyses will follow CONSORT guidelines (Campbell, Piaggio, Elbourne, & Altman, 2012; Piaggio et al., 2012; Schulz, Altman, & Moher, 2010; Zwarenstein et al., 2008). Outcomes will be described by arm using summary statistics. Baseline characteristics will be compared by study arm and by cluster study to ensure that the pragmatic allocation of health facilities and sequential rollout of the study did not introduce significant bias. Baseline characteristics which will differ between treatment arms within and over all clusters will be described using summary statistics.

Since the documentation of final treatment in both arms is part of the per protocol definition, only the PP population can be used for primary outcome analysis. The primary outcome will be evaluated using a random effects logistic regression model with the binary outcome variable of antibiotic prescription, with study arm and covariates at patient-level (e.g. age, sex) as fixed effects, and cluster (health facility) and patient included as random effects. Binary secondary outcomes will be evaluated in the same way. All estimates will be reported as odds ratios (ORs) with two-sided 95% confidence intervals (CI). The study will be deemed a success if antibiotic prescription at the initial consultation is 25% less in the ePOCT+ arm compared to the control arm, although we expect a greater reduction based on limited pilot data.

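### Superiority and success are set at a 25% relative reduction, but the stated 80% power is for a test of no difference, and the plan does not say which rule decides or which estimate is judged

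*SAP*

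**What the plan says.** **The 25% rule.** Protocol 9.1 reads "Superiority in antibiotic prescription is defined as a relative decrease of" at least 25%, and SAP 3.3 puts that threshold on the decrease "in the proportion of children prescribed an antibiotic". The synopsis has the same definition. SAP 6.1, in the analysis section, turns 25% into the criterion for success: "The study will be deemed a success if antibiotic prescription at the initial consultation is 25% less in the ePOCT+ arm". It adds "although we expect a greater reduction based on limited pilot data", without giving a size.

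**The test of no difference.** SAP 3.3 sizes the trial this way: "To have 80% power to detect a 25% reduction in antibiotic prescription (from 35% to 26%), for a two-sided hypothesis test at alpha of" 0.05, needing at least 11 clusters per arm, with 16 planned. Protocol 9.2 plans a significance test comparing the two proportions and their 95% confidence intervals.

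**The scale at analysis.** SAP 6.1 fits a logistic model with random effects for facility and patient and reports its estimates as odds ratios with two-sided 95% intervals. It also says "Outcomes will be described by arm using summary statistics", so crude proportions will be available.

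**Alpha.** The synopsis gives one-sided 0.025 and SAP 3.3 gives two-sided 0.05, which share a critical value. Protocol 9.1 differs: "for a one-sided hypothesis test at alpha of 0.05, we would require a minimum of 11 clusters per arm".

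**The concern.** The plan contains two rules for the primary outcome and does not relate them. A significance test asks whether the reduction differs from zero. The superiority definition and the success sentence ask whether it is at least 25%. Nothing says whether both are needed, or what is concluded when the reduction is significant but smaller than 25%.

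The power sentence directly follows the superiority definition and speaks of detecting a 25% reduction. A reader could easily take 80% as the chance of meeting the 25% rule.

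The estimate to be judged is also open. Allocation is not randomised, and SAP 6.1 allows adjustment for baseline imbalance, so crude and adjusted reductions may differ. An odds ratio cannot be read directly against a threshold set on proportions. At stake is whether the verdict on the primary outcome is fixed before the data are seen.

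**Working it through.** **Inputs** (SAP 3.3): control 35%, intervention 26%, cluster size 660, ICC 0.025, 80% power, two-sided alpha 0.05, 16 clusters per arm. Note that 35% to 26% is a 25.7% reduction; exactly 25% would be 26.25%.

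**1. Reproduce the 11 clusters.** Design effect = 1 + 659 × 0.025 = 17.475. For a test of zero difference, n per arm = (1.960 + 0.842)² × (0.35 × 0.65 + 0.26 × 0.74) / 0.09² = 406.9. Clusters = 406.9 × 17.475 / 660 = 10.77, so 11 (10.86 with pooled variance). The stated figure is recovered with a null of no difference, so the 80% belongs to that test.

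**2. Both rules at 16 pooled clusters.** Effective n per arm = 16 × 660 / 17.475 = 604.3.
- Significance: Φ((p1 − p2)/SE − 1.96). For 35% against 26%, SE = √(0.4199/604.3) = 0.0264, giving Φ(3.41 − 1.96) = 93%.
- Observed reduction at least 25%: Φ((ln 0.75 − ln RR)/SE of log RR), where that SE = √[(1−p1)/(n·p1) + (1−p2)/(n·p2)] = 0.0882. This gives Φ((−0.2877 + 0.2973)/0.0882) = Φ(0.11) = 54%.

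The last column comes from a beta-binomial cluster simulation (40,000 runs, cluster-level t test).

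| True reduction | Significant | Observed ≥ 25% | Significant but < 25% |
|---|---|---|---|
| 25% | 91% | 50% | 39% |
| 35% to 26% | 93% | 54% | 36% |
| 30% | 98% | 78% | 19% |
| 35% | >99% | 94% | 6% |
| 40% | >99% | 99% | 1% |

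An 80% chance of observing at least 25% needs a true reduction of about 30.5%. The 54% is not sensitive to the ICC: 56.5% at 0.01 and 53.1% at 0.05.

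**3. Where the rules disagree.** At 16 pooled clusters the smallest significant observed reduction from 35% is about 15% (15.0% normal, 15.7% with t on 30 df). Results between about 15% and 25% pass one rule and fail the other.

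**4. Scale.** At 35% control, a 25% reduction is an odds ratio of (0.2625/0.7375)/(0.35/0.65) = 0.66. An odds ratio of 0.75 gives odds of 0.75 × 0.5385 = 0.4038, a proportion of 28.8%, which is only an 18% reduction. These are marginal odds ratios; the planned model's are conditional on facility and patient and differ further.

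**5. Alpha in Protocol 9.1.** One-sided 0.05 replaces 1.960 by 1.645: 320.5 × 17.475 / 660 = 8.49, so 9 clusters (up to 10 with a continuity correction or t-based formula). At 11 clusters it gives about 88% power, not 80%.

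**The case against.** **The rules can coexist.** A trial may require significance for the inference and a minimum worthwhile reduction for calling the programme a success. That is a legitimate choice, and a result that is significant but short of success is then coherent. This stands. What is missing is the sentence that says so, and the power of the second rule.

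**The 50% is built in.** Any point threshold set at the true effect is met about half the time. True; the figure shows only that 80% is not that rule's power.

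**A larger effect is expected.** SAP 6.1 says so, and Protocol 1.5 reports 84% to 15% and 95% to 11% for earlier generations of the tool. If the true reduction is 35% or more, the conflict nearly vanishes. But SAP 6.1 gives no size and calls the pilot data limited, and the earlier results came from Tanzania, under controlled research conditions and from much higher control rates than 35%.

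**The disagreement depends on pooling.** With 5 clusters per arm at a true 25% reduction, significance has about 46% probability and the 25% rule 50%; with 6 per arm, 53% and 50%. The 15% to 25% band then essentially disappears. This also stands. The single model in SAP 6.1 favours pooling, whereas Protocol 4.1 compares within blocks; that conflict is a separate issue.

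**Two stronger readings are tempting and not supported.** A reader might infer that the 95% confidence limit must exclude reductions below 25%, which would be met only about 3% of the time at the planned effect. No section gives a margin, a shifted null or a confidence-limit condition, so this carries little weight. A reader might also infer that an odds ratio of 0.75 would count as success. SAP 3.3 sets the threshold on proportions, so that would be a misreading, although reporting only odds ratios invites it.

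**Conclusion.** The point holds. The threshold that the documents use for superiority and success has no stated power, and the stated 80% belongs to a different rule. At the planned effect with 16 pooled clusters per arm, the chances are about 93% for significance and 54% for an observed reduction of at least 25%, and roughly a third or more of trials would meet the first and miss the second. Discordance falls to about 6% at a true 35% reduction and 1% at 40%.

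These figures assume 35% control, ICC 0.025, equal clusters of 660, pooling over the three blocks and a normal approximation; t-based power for significance is slightly lower (91%). The sample size itself is not wrong under the SAP's inputs. On scale, the gap is narrow: the threshold is defined on proportions, but the estimate compared with it is not named. The alpha conflict is a correction to Protocol 9.1 and changes no planned test.

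**What to change.** 1. Use one rule in the synopsis, Protocol 9.1, SAP 3.3 and SAP 6.1. Either:
   - (a) define superiority as the two-sided 95% confidence interval excluding no difference, with 25% kept as the planning effect and a reported benchmark; or
   - (b) keep 25% as the success rule, stating that it applies to the estimated relative reduction in proportions, whether significance is also required, and that 80% is not that rule's power (about 50% to 54% at the planned effect).
2. Report the risk ratio with its confidence interval beside the odds ratio, and name it as the estimate compared with 25%.
3. Correct Protocol 9.1 to one-sided 0.025, equivalent to two-sided 0.05.

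The cost is wording in four places and one extra reported estimate, with no extra patients and no change to the fitted model. A model-based risk ratio does need a specified standardisation and interval method. Under (b), the stated power becomes less favourable.

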## 2 STUDY OBJECTIVES AND THEORY OF CHANGE

The **goal** of this study is to mitigate AMR using a novel dynamic ePOCT+ tool that helps front-line HWs manage sick patients, enhanced by additional digital platforms to promote uptake, sustainability, and integration of the tool into the health system. More specifically, this study seeks to:

### 2.1 Objective 1

**Improve the integrated management of children with an acute illness** (more specific and diverse diagnoses; reduced antibiotic prescriptions) through the provision of an electronic CDSA (ePOCT+) to clinicians working at primary care level.

*Hypothesis 1:* The use of ePOCT+ in the outpatient PHC setting in Rwanda will result in decreased prescription of antibiotics while maintaining similar clinical outcomes.

*Hypothesis 2:* The use of ePOCT+ in the outpatient PHC setting in Rwanda will result in improved quality of care.

### 2.2 Objective 2

**Improve the diagnostic and prognostic accuracy of the clinical algorithm across spatiotemporal variations in epidemiology and resources** through machine learning analyses of the data generated through the ePOCT+ tool, checked by clinical experts.

*Hypothesis 3:* Modifications in the electronic CDSA based on the results of ML analyses will enable similar or better outcomes over the course of the study despite temporal and spatial variability in disease patterns and/or availability of resources.

### 2.3 Objective 3

**Enhance the health management information system for monitoring and evaluation and supportive supervision** (increased number of meaningful indicators that are reviewed and actioned regularly) through additional data analysis and visualization of patient-level data generated by the ePOCT+ tool.

*Hypothesis 4:* The patient-level clinical data that is visualized and analyzed in near real-time will lead to improved ability of the DHMT to monitor the quality of patient care and undertake targeted supportive supervision of HFs and HWs.

*Hypothesis 5:* The patient-level clinical data that is visualized and analyzed in near real-time will lead to a more accurate epidemiological profile of the district and improved spatial and temporal resource allocation.

### 2.4 Objective 4

[figure not shown]
**Create a framework for the implementation of dynamic clinical decision support algorithms and supporting tools**, for large-scale, sustainable, and clinically responsible use of machine learning and data science in digital health.

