In Phase 2, the same outcome indicators as in Phase 1 will be measured and evaluated over time to monitor longitudinal changes in the effectiveness of the intervention. The medical content of the algorithm will not be fixed anymore, but rather modifiable. Each potential modification will first be evaluated by the Rwandan clinical expert group for its clinical coherence, safety and potential benefit and then applied to the retrospective data. If retrospective analyses confirm a clinically relevant positive impact (or resource saving), the modification will be implemented in the relevant locations and/or patient sub-groups.

Health facilities will need to demonstrate successfully meeting the objectives of Phase 1 before entering Phase 2. In case of any deviations from expected outcomes, or any issues that preclude reaching the study objectives as part of the parallel cluster study in Phase 1, design and implementation will be re-evaluated. In this case, Phase 1 would continue in modified form instead of moving on to Phase 2. Regardless of study phase, outcomes will be continuously monitored in all facilities, and if outcomes are not trending as expected, the causes will be investigated as part of routine monitoring of study implementation by the research team in collaboration with the DHMT.

**Figure 6:** Study design overview

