1.1 Hypothesis

In routine conditions, health workers (HWs) provided with an electronic clinical decision support algorithm (CDSA) on tablets or PCs can treat sick children attending primary health care facilities in Rwanda with appropriate antimicrobial prescriptions. More specifically, we hypothesize that with the use of CDSA called electronic point of care tests plus (ePOCT+) for case management of sick children in primary health care facilities, compared to routine care, less antibiotics will be prescribed at the initial consultation.

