2.1.2 Secondary outcomes

All secondary outcomes are compared between the intervention (ePOCT+) and control (routine care) arms.

Percentage of children cured at day 7 in the intervention group (ePOCT+) as compared to the control group (routine care)

Outcome measure: The child is defined as being cured at day 7 if the caregiver says that the child is cured or has improved since the initial consultation. Non-referred secondary hospitalizations (if caregiver says that child was hospitalized between day 0 and day 7 but the electronic clinical data does not indicate a referral for hospitalization) will however be considered as clinical failures even if the child is already cured at day 7.

Timing and method of measurement: Assessment of subjective clinical cure by the caregiver, and history of non-referred hospitalization will be assessed by telephone or home visit follow-up 7 days (range 6-14 days) after enrollment of the subject. The day of enrollment of the subject is considered as day 0.

Analysis type: Superiority

Secondary consultations:

- % of children with one or more unscheduled re-attendance visits at any health facility by day 7

Timing and method of measurement: Telephone or home visit follow-up 7 days (range 6-14 days) after enrollment of the subject. The day of enrollment of the subject is considered as day 0.

Severe outcome by day 7:

- % of children with non-referred secondary hospitalization by day 7
- % of children who have died by day 7

Timing and method of measurement: Death and non-referred secondary hospitalization will be assessed by telephone or home visit follow-up 7 days (range 6-14 days) after enrollment of the subject. The day of enrollment of the subject is considered as day 0.

Primary referrals:

- % of children referred to hospital or inpatient ward at a health centre at initial consultation

Timing and method of measurement: Documented by the HW at the end of the initial consultation in the eCRF (control arm) or in ePOCT+ (intervention arm) when the subject was enrolled (day 0)

Appropriate case management for malaria at initial consultation

- % of febrile children tested for malaria by RDT and/or microscopy at day 0
- % of malaria positive children (positive RDT result OR positive microscopy result) prescribed an antimalarial at day 0
- % of malaria negative children prescribed an antimalarial at day 0
- % of untested children prescribed an antimalarial at day 0

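### The SAP's success rule rests on antibiotic prescribing alone, and no prespecified rule decides the similar-clinical-outcomes half of the protocol's Hypothesis 1

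*SAP*

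**What the plan says.** **Success rule.** SAP 6.1: "The study will be deemed a success if antibiotic prescription at the initial consultation is 25% less in the ePOCT+ arm". No condition on cure, hospitalisation or death is attached there or elsewhere in the SAP.

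**Hypotheses.** Protocol 2.1, Hypothesis 1, states that ePOCT+ "will result in decreased prescription of antibiotics while maintaining similar clinical outcomes". SAP 1.1 keeps only the first half: "compared to routine care, less antibiotics will be prescribed at the initial consultation". The SAP 1.2 objective for Phase 1 and the primary aim in protocol 7.1 are also confined to antibiotics.

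**Day-7 cure.** Protocol 9.1 describes the planned size as "sufficient to test for non-inferiority in the secondary outcome (clinical cure at day 7) between the control and intervention groups", and the synopsis says the same. SAP 2.1.2 gives cure the label "Analysis type: Superiority". Neither document states a margin. Non-referred hospitalisation and death by day 7 are further secondary outcomes.

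**Safeguards.** SAP 3.4 limits the interim analyses to the primary endpoints, and the SAP's only primary outcome is antibiotic prescription. Termination for harm (SAP 3.4, protocol 11.4) is left to the Principal Investigators, with no cure threshold. Protocol 4.1 says of the next phase: "Health facilities will need to demonstrate successfully meeting the objectives of Phase 1 before entering Phase 2". It then provides for re-evaluation, with Phase 1 continuing in modified form, if outcomes deviate from what was expected.

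**The concern.** A fall in prescribing is a benefit only if the children do no worse, and the protocol builds that into its first hypothesis. The SAP's decision sentence omits it. If the plan is followed exactly, a result that contradicts half of Hypothesis 1 can be labelled a success.

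This is distinct from the conflict between the superiority and non-inferiority labels. Correcting the label alone would leave the success sentence as it is, with the cure result outside the verdict.

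Phase 1 is also where clinical outcomes are compared with controls. Protocol 11.2 notes that Phase 2 has no control group, and the synopsis says cure, secondary hospitalisation and death may not be collected then.

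**Working it through.** **1. The plan's own figure.** Inputs from SAP 3.3: 35% against 26%, two-sided alpha 0.05, 80% power, 660 children per cluster, ICC 0.025.
- Individually randomised size: 410 per arm.
- Design effect: 1 + (660 − 1) × 0.025 = 17.475.
- Clusters: 410 × 17.475 / 660 = 10.86, so 11 per arm as stated. Power is 80.6% with 11 clusters and 92.6% with 16.

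**2. What the success verdict depends on.** The SAP does not say whether the 25% applies to the point estimate or to a confidence limit, and its model reports odds ratios. I read it here as a point estimate on the risk-ratio scale. With control rate 0.35, intervention rate p and effective size 16 × 660 / 17.475 = 604 per arm:

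P(success) = Φ[(0.75 × 0.35 − p) / √V], where V = [p(1 − p) + 0.75² × 0.35 × 0.65] / 604.

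| True relative reduction | p | P(success) |
|---|---|---|
| 25% | 0.2625 | 50% |
| 30% | 0.245 | 78% |
| 35% | 0.2275 | 94% |
| 40% | 0.21 | 99% |

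No cure term appears. For example, an observed fall from 35% to 26% is a relative fall of 9/35 = 25.7%. It meets the rule whether day-7 failure stays at 3% or rises to 6%.

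**3. Power of a cure condition.** SAP 6.1 expects 3% not cured and cites 13–25% loss to follow-up, with midpoint 19%. Followed per cluster: 660 × 0.81 ≈ 535. Per arm: 16 × 535 = 8,560. The documents give no ICC for cure, so I assume 0.005 to 0.025; the upper end is the only ICC they state, which is for antibiotics.
- Design effect: DE = 1 + 534 × ICC.
- Standard error with 3% failure in both arms: SE = √[2 × 0.03 × 0.97 × DE / 8,560].
- Chance of excluding margin M: Φ(M/SE − 1.96).

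| Cure ICC | DE | SE | M = 2 points | M = 3 points |
|---|---|---|---|---|
| 0.005 | 3.67 | 0.00500 | 98% | 100% |
| 0.01 | 6.34 | 0.00657 | 86% | 99.5% |
| 0.02 | 11.68 | 0.00891 | 61% | 92% |
| 0.025 | 14.35 | 0.00988 | 53% | 86% |

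The loss rate matters little because clustering dominates. At ICC 0.025 and a 2-point margin, 13% and 25% loss give 52.8% and 52.4%.

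**4. Would worse cure be noticed?** For failure of 3% against 6%, SE = √[(0.03 × 0.97 + 0.06 × 0.94) × DE / 8,560]. The chance that the two-sided 95% interval excludes zero is 99.9%, 96%, 79% and 71% at ICC 0.005, 0.01, 0.02 and 0.025. For a fall in cure from 97% to 96%, the superiority test has about 46% power at ICC 0.005 and 15% at 0.025. A non-significant superiority result therefore does not show that outcomes are similar.

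**The case against.** The SAP is consistent with itself. Its hypothesis, its objective and the protocol's primary aim concern antibiotics only, and defining success by the single primary outcome, with safety reported as secondary, is conventional. Cure, non-referred hospitalisation and death are all prespecified and reported with 95% intervals, and step 4 shows that a doubling of failure would probably be flagged. This stands, and it limits the severity. It does not close the gap, because the protocol's hypothesis is joint and reporting is not a decision rule.

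Three stronger readings are tempting, and the documents do not support them.
- *Success opens Phase 2.* Protocol 4.1 never cites the 25% rule. It refers to the objectives of Phase 1, and protocol Objective 1 carries Hypothesis 1. It also provides for re-evaluation instead of progression when outcomes deviate. SAP 1.2 states the Phase 1 objective as antibiotics only, so the link can be inferred, but it is not written. Worse cure could block Phase 2 as the text stands.
- *The trial cannot answer Hypothesis 1.* The cure data are collected and an estimate with its interval will be reported. What is missing is a rule for judging it.
- *The joint rule should also be the Phase 2 gate.* That gate is worded for individual facilities. A between-arm interval cannot be applied to one facility with about 535 followed children and about 16 failures (535 × 0.03).

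**Conclusion.** The concern holds as a gap between the SAP and the protocol, and it should be fixed. The success verdict depends on antibiotic prescribing alone. Worse cure would be reported and could lead to discretionary action, but it cannot alter that verdict, and nothing prespecified settles whether clinical outcomes were similar.

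The absence of a cure condition is read directly from the text and needs no assumption. The power figures assume equal true failure of 3%, 19% loss, 16 equal clusters per arm, a normal approximation, and a cure ICC that the documents do not supply. On those terms a 3-point margin is feasible across the ICC range shown, while a 2-point margin is comfortable only if the cure ICC is near or below 0.01. The margins of 2 and 3 points are illustrations, not recommendations.

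**What to change.** 1. Reword the success sentence in SAP 6.1 so that Hypothesis 1 is declared supported only if (a) the antibiotic criterion is met **and** (b) the cluster-adjusted two-sided 95% confidence interval for the difference in day-7 clinical failure, intervention minus control, lies below a margin fixed and justified by the clinical team before data are seen.
2. If only (a) holds, report: *prescribing reduced, similar clinical outcomes not established*.
3. Change the SAP 2.1.2 label for cure from superiority to non-inferiority, to match protocol 9.1 and the synopsis.
4. State how the risk difference and its interval will be obtained, since SAP 6.1 plans odds ratios only.

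**Cost.** Wording in the SAP, and agreement on a margin. No added patients and no extra data collection. No alpha split is needed, because both conditions must hold. The price is power: the chance of the joint claim cannot exceed the chance of meeting (b), which may be as low as 53% for a 2-point margin or 86% for a 3-point margin if the cure ICC is 0.025.
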